10.3 ANALYSIS DATASETS

The safety population will include all randomized participants that receive any study drug defined by treatment they actually received (either of the SL-BUP or XR-NTX treatments or placebo).

Analyses of efficacy outcome measures will be done using an intention to treat (ITT) population defined by the randomization irrespective of whether any study drug/placebo was actually received.

10.4 DESCRIPTION OF STATISTICAL METHODS

10.4.1 GENERAL APPROACH

All statistical computations will be performed by biostatisticians at the PASA Consortium data coordinating center [part of the Research Triangle Institute (RTI)]. For summaries of study data, categorical measures will be summarized in tables listing the frequency and the percentage of participants; continuous data will be summarized by presenting mean, standard deviation, median and range; and ordinal data will be summarized by only presenting median and range. P-values presented will be based on two-sided tests unless otherwise specified and generally adjusted for randomization factors. For continuous outcomes, checks of normality will be performed and if required, transformations or non-parametric tests will be employed. Additional details for potential covariate adjustments in secondary analyses or handling violations of analytic method assumptions will be detailed in the statistical analysis plan.

The analyses will include all available observations (i.e., from the various assessment times) from each participant. The Mixed-Effects Model of Repeated Measures (MMRM) provides valid inference under the assumption of ignorable missingness. No imputation processes will be used to replace missing data. However, every effort will be made to minimize missing data. Because missing observations have the potential to alter the results of analyses, we will examine whether the pattern of missing data is different among the groups. We will also examine the distribution of baseline covariates between those with and without missing outcome data. If there are no systematic differences between those with and without missing data, the data will be considered to be missing at random. If there are significant differences in dropout or missing data patterns between treatment arms, we will conduct sensitivity analyses to determine the impact of missing information on the treatment comparisons.

10.4.2 ANALYSIS OF THE PRIMARY EFFICACY ENDPOINT(S)

The primary dependent variable will be response status at Week 8 for each participant. A positive response is defined as a decrease from baseline of at least 8 points on the CAPS-5 score and a reduction of at least 1 risk level of alcohol use, as defined by WHO, at Week 8. Response data will be analyzed using mixed logistic regression with treatment group, measurement visit as a categorical variable, gender, site, presence/absence of anti-depressants, and other potential confounders as explanatory variables. A treatment group by measurement visit interaction will be included to account for the longitudinal nature of the data with the Week 8 effect being the primary outcome of interest. A two-sided p-value will be reported from the primary analysis for the all pairwise comparisons of SL-BUP/XR-NTX treatment and placebo groups.

As a complement to the primary outcome, the AUD and PTSD components of the composite will be evaluated individually. Difference in heavy alcohol use at Week 8 (defined as *>4 standard drinks/sessions for men and >3 standard drinks/sessions for women*) will be analyzed using a generalized-linear mixed model with treatment group, gender, site, presence/absence of anti-depressants, and other potential confounders as explanatory variables. Difference in reduction of PTSD symptoms at Week 8 (as measured by the CAPS-5) will be analyzed using a generalized-linear mixed model with treatment group, gender, site, presence/absence of anti-depressants, and other potential confounders as explanatory variables. For both outcomes, a treatment group by visit interaction term will be included to account for the longitudinal nature of the data, with Week 8 effect being the primary outcome of interest.

10.4.3 ANALYSIS OF THE SECONDARY ENDPOINT(S)

SL-BUP/XR-NTX treatment will be compared with the PLACEBO (PLC) group for the following secondary outcomes:

- Examine differences in baseline psychophysiological measures, severity of PTSD and AUD, and treatment outcomes.
- Examine whether BUP/NTRX improve psychophysiology measures at 8 Weeks (primary endpoint).

- Examine whether the degree of change from baseline to 2-week psychophysiological measures are associated with AUD and PTSD outcomes at Week 8.

*Psychophysiological assessments are optional to not be a barrier to enrollment or randomization.

Continuous data will be analyzed using MMRM with treatment group, gender, site, presence/absence of concomitant antidepressants, and other potential confounders as between-participant factors and visit (categorical) as a within-participant repeated measure. The model will also include the two-way interaction between treatment group and visit. When appropriate, significant differences between treatment groups will be further analyzed with post-hoc comparisons. Adjusted marginal means (also called LS means) will be used to report and test for differences in mean change at Week 8 for the placebo and SL-BUP/XR-NTX groups providing 95% confidence intervals and a p-value for the difference between them.

10.4.4 SAFETY ANALYSES

The safety analyses population includes all randomized participants. These analyses will include those participants who have reported an adverse event as well as those who do not report an adverse event. The incidence of treatment emergent adverse events, type of adverse events, and frequency of withdrawals due to an adverse event will be summarized by treatment group. Appropriate statistical comparisons will be made between treatment groups in terms of 1) rates of adverse events, 2) discontinuation due to adverse events, and 3) side effect scales. Rates will be compared using time to event hazard analysis. Frequencies will be analyzed using the chi square or Fisher Exact test. The scales will be examined using non-parametric analyses when appropriate. This study is not powered as an equivalence study so the non-significance of differences between groups does not truly imply equivalence.

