10.5 SAMPLE SIZE

The sample size for a proof-of-concept study should be large enough to be able to detect a drug effect or surrogate signal, but at the same time expose a minimum number of participants to an experimental drug combination in a reasonable timeframe within a restricted budget. Sample size was determined based on sample sizes used in similar double-mask, placebo-controlled studies of AUD and PTSD, and based on the estimated recruitment rate over the allotted enrollment timeline.

With these factors in mind, we plan to enroll approximately 180 participants to allow for screen failures/dropouts prior to randomization.

With respect to sample size, the goal is to obtain at least 90 participants randomized to either of the two retained arms (XRNTX/2mg BUP arm and PLACEBO arm). Recruitment will occur over a 24-month enrollment period. If this goal is met with time left in the enrollment period, sites will be allowed to randomize additional participants but will not exceed the original planned sample size of 135 randomized participants across all 3 originally planned study arms.

To ensure balance within each treatment group we will use stratified randomization on site, presence/absence of concomitant antidepressants, and gender. We plan to use blocking within each stratum of the randomization scheme to balance treatment assignments. We estimate that attrition will be approximately 30%. However, all randomized participants will remain in analysis (intent-to-treat) regardless of how long they participate in the study.

For the primary outcome, we assume 90 randomized participants (allowing for screen failures/dropouts) allotted equally among the two study arms and with the success rates shown in the below table. We calculated power for two by two contingency tables for comparisons with each treatment arm and the Placebo arm using a Fisher's Exact test with the Walters approximation applying a nominal two-sided alpha level of 0.05.

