8.2 Protocol Deviations

Protocol deviations will be listed with information such as type of deviation, time of occurrence, and reason. Incidence of protocol deviations will also be summarized overall and for each protocol deviation category. Incidence rate of protocol deviations will be calculated as the number of deviations divided by number of participant days.

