Phosphatidyl ethanol (PEth)	Continuous (range between 0 and >210 ng/mL)	
Phosphatidyl ethanol (PEth) are a series of abnormal phospholipids located in the cell membrane and formed in the presence of ethanol and phospholipase D. PEth serves as a biomarker of alcohol ingestion in the past 2-3 weeks using liquid chromatography tandem mass spectrometric assessment of human blood (whole or dried spots). PEth in blood is often used as a marker of chronic alcohol use and was collected at baseline and weeks 8 and 12.
 
At the present time, the international scientific community has not yet established a cut-off value for PEth concentration in blood to be used for differentiating an acceptable social ethanol intake (<40 g for males and <20 g for females, according to the WHO parameters), from an at-risk-alcohol-use (40–60 g/die) and chronic excessive drinking behavior (>60 g/die). However, per LabCorp, PEth levels in excess of 20 ng/mL are considered evidence of moderate to heavy ethanol consumption.

Safety Outcomes		
Adverse Events	Counts and proportions	Total number and proportion of treatment emergent adverse events. Comparison of AE rates by treatment group will also be stratified by type and severity.
Withdrawals due to Adverse Events	Proportion	Proportions of individuals by treatment group who withdrew from the study due to adverse events
Adherence and Retention Outcomes		

Variable	Type	Definition
Serum Buprenorphine and Norbuprenorphine	Continuous	
Buprenorphine and its metabolite norbuprenorphine are assayed using liquid chromatography tandem mass spectrometry by a commercial laboratory. Sample results are available via the commercial laboratory portal using a study specific username/password combination and the unique participant code/requisition number.
 
To assess medication adherence, blood samples collected at study weeks 8 and 12 will be tested for buprenorphine and its metabolite, norbuprenorphine, using quantitative assessments.

Pill Count	Count and proportion	
A dosing log case report form (CRF) is completed weekly (or since the last in-person visit) for each participant. The number of completed NTX injections received (at baseline, week 4, and week 8) is recorded, as well as the number of missed SL-BUP pills per week. For each medication (NTX and SL-BUP), the proportion of subjects who missed any treatment will be derived, as well as the total number of missed injections or pills, per participant.

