9.5 Safety Analysis Methods

9.5.1 Adverse Events

Any AEs will be listed and summarized by system organ class and preferred event term. Summaries will include the number of individuals experiencing events over the duration of the study. These summaries will be created for all AEs and AEs by severity (mild or moderate vs. severe or greater). Summaries will be provided by treatment group. If models can be run, point and confidence interval estimates of the risk difference will be obtained by modeling the probability of experiencing at least one adverse event. The model is specified with the equation:

$$g(E(Y_{ij})) = \beta_0 + \beta_1 \text{Treatment}_{ij} + s_i + \varepsilon_{ij}$$

Where $g(E(\cdot))$ indicates the identity link function on the expected value of Y , Y_{ij} is the occurrence of an AE outcome (any AE, any SAE, and any related AE) in subject i , β_0 is the intercept, β_1 is the treatment group coefficients, s_i is a random subject effect, and ε_{ij} is the residual error term.

Point and confidence intervals for the difference in experienced AE proportion between treatment groups will be estimated with a generalized linear mixed model (GLMM), assuming a binomial distribution and identity link. GLMMs are a flexible generalization of the linear mixed effect model that allows response outcomes to have an error distribution other than the normal distribution (McCullagh, & Nelder, 1989). Statistical analysis modeling will be carried out utilizing SAS/STAT PROC GLIMMIX (SAS Institute Inc. 2017) with the general structure of the SAS code for this model is listed below:

```
proc glimmix data=anlyaedata;
  class patient treatment;
  model any_ae = treatment / link=identity dist=binomial;
  random int / subject=patient;
run;
```

A similar model will be run for the difference in proportion of withdrawn subjects due to adverse events between treatment groups. If the above specified models cannot be fit due to limitations of the study data, frequencies will be analyzed using chi-square test.

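### The SAP omits, without explanation, the time-to-event comparison of adverse events that the protocol plans, and keeps only counts and proportions although about 30% attrition is expected

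*Protocol*

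**What the plan says.** Protocol 10.4.4 (Safety Analyses) sets out two methods side by side. For rates: "Rates will be compared using time to event hazard analysis". For frequencies: "Frequencies will be analyzed using the chi square or Fisher Exact test".

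SAP 9.5.1 (Adverse Events) carries only the second kind forward. Where models can be fitted, its plan reads as follows: "point and confidence interval estimates of the risk difference will be obtained by modeling the probability of experiencing at least one adverse event". Any AE, any SAE and any related AE are the outcomes modelled. If they cannot be fitted, "frequencies will be analyzed using chi-square test". SAP 9.2 defines the AE outcome in the same terms: "Total number and proportion of treatment emergent adverse events". No AE analysis in the SAP uses time to event or person-time, and the SAP version log does not mention the omission.

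Three other places bear on this:
- The primary safety objective in SAP 3.1.1 asks whether AE rates differ between the arms.
- Protocol 10.5 says "We estimate that attrition will be approximately 30" per cent, and SAP section 6 repeats the figure. Neither splits it by arm.
- SAP 8.2 does use person-time, but for deviations: "Incidence rate of protocol deviations will be calculated as the number of deviations divided by number of participant days".

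**The concern.** A proportion with at least one AE treats everyone as observed for the same length of time. With substantial attrition that need not be true: a participant who leaves at Week 3 has less time to report an event than one followed to Week 14. The hazard comparison in the protocol allows for this and the analysis in the SAP does not. Protocol 10.1 says the analysis will be guided by the SAP, so the hazard comparison may simply not be run.

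Two things are at stake. If follow-up differs between the arms, the crude proportions can show a difference that is not there, or shrink one that is. Even if follow-up is equally incomplete in both arms, a true difference is somewhat diluted. The missing-data section (SAP 7.3) names the primary and exploratory outcomes and does not mention safety, so it does not fill the gap.

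**Working it through.** The plan gives no AE risk, no power for safety and no attrition by arm, so there is no figure of its own to reproduce here. What follows is an illustration.

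**Inputs from the documents.** Overall attrition about 30% (Protocol 10.5, SAP 6); AE collection from first dose to Week 14 (Protocol 8.3); 45 per arm (Protocol 10.5).

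**Assumptions.** Constant AE hazard; constant dropout hazard, unrelated to AEs; AE capture ends at dropout; true 14-week AE risk *q* between 10% and 90%; dropout *d* averaging 30% over the two arms.

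**Formula.** Let L = −ln(1−q) and K = −ln(1−d) be the cumulative hazards over 14 weeks. The expected observed proportion with an AE is

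L/(L+K) × [1 − (1−q)(1−d)].

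**No true difference, q = 50%** (L = 0.693):
- d = 40%: K = 0.511, so 0.693/1.204 × (1 − 0.5×0.6) = 0.576 × 0.70 = 40.3%.
- d = 20%: K = 0.223, so 0.693/0.916 × (1 − 0.5×0.8) = 0.756 × 0.60 = 45.4%.
- Difference: −5.1 points for the arm with more dropout.
- d = 30% in both arms: 42.9% versus 42.9%, difference 0.

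A different dropout model gives the same size. With exits spread evenly over 12 weeks and hazard ln2/14 per week, the observed proportions are 44.9% at 20% dropout and 39.8% at 40%, again 5.1 points.

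**Range over true AE risk** (higher-dropout arm minus the other, in points):

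| True 14-week risk | 30/30 | 35/25 | 40/20 | 50/10 |
|---|---|---|---|---|
| 10% | 0 | −0.6 | −1.1 | −2.2 |
| 30% | 0 | −1.6 | −3.2 | −6.5 |
| 50% | 0 | −2.5 | −5.1 | −10.2 |
| 70% | 0 | −3.3 | −6.5 | −13.2 |
| 90% | 0 | −3.5 | −6.9 | −14.0 |

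**Where the effect vanishes or shrinks.**
- If participants leave only after a first AE, the simulated difference is 0.000, with a rejection rate of 0.050.
- If all AE risk (50%) falls in the first two weeks, a 40/20 split gives 48.4% versus 49.3%, or −0.9 points.
- If the window is 8 weeks, as in SAP 3.1.1, with the same hazard and exits spread over 12 weeks, the proportions are 28.6% versus 30.7%, about −2.0 points.

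**Effect on tests** (2,000 simulated trials, 45 per arm, two-sided 0.05):

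| Scenario | Dropout | Proportion test rejects | Log-rank rejects |
|---|---|---|---|
| No difference, 50% risk | 30/30 | 0.047 | 0.054 |
| No difference, 50% risk | 40/20 | 0.065 | 0.044 |
| No difference, 50% risk | 50/10 | 0.149 | 0.052 |
| True 60% vs 40% | 30/30 | 0.39 | 0.44 |
| True 60% vs 40% | 40/20 | 0.23 | 0.45 |
| True 60% vs 40% | 50/10 | 0.12 | 0.42 |

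In the last three rows the larger dropout is in the arm with more AEs, and the expected observed difference is 17.7, 12.6 and 7.4 points against a true 20.

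**The case against.** The case against is strong on several points.

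*Proportions were always planned.* The protocol puts frequency tests next to the hazard analysis, so a reader who infers that the SAP swapped one method for another goes too far. The SAP omits one of two. This stands.

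*Unequal loss is not predicted.* A reader might infer that the arm losing more participants will look safer and that harm from the active treatment will be hidden. The documents do not support that. The 30% is one overall figure, and an equal split favours neither arm. A participant who leaves because of a first side effect has already been counted as having an AE, and the SAP separately compares withdrawals due to AEs. This stands for any AE. It is weaker for SAEs and related AEs, which the SAP also models: leaving after a mild or unrelated event removes time at risk for a later one.

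*Attrition is not defined as loss of AE follow-up.* Participants may stop medication and stay for assessments (Protocol 7.3.4). Early exits have closing procedures, and a post-study call or visit covers AEs (Protocol 5.4.2). The illustration therefore leans towards too much loss. Some loss remains, because no data are collected once consent is withdrawn (Protocol 5.4.2).

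*Size against noise.* With 45 per arm and proportions near 40% and 45%, the 95% half-width is about 1.96 × √(0.398×0.602/45 + 0.449×0.551/45) = 20 points, so a 5-point bias would be hard to see in a single trial. The protocol also warns that a non-significant safety result does not show equivalence.

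*The word rate is used loosely.* SAP 9.2 speaks of AE rates under an outcome typed as counts and proportions, so the objective in SAP 3.1.1 does not by itself require person-time. This stands; the firmer ground is the explicit method in Protocol 10.4.4.

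**Conclusion.** The point holds as an unexplained omission: the protocol names a time-to-event comparison of AE rates, and the SAP neither contains it nor says why. That does not depend on any assumption.

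The statistical consequence does. It needs AE follow-up that is shorter in one arm for reasons largely unrelated to AEs. Under an assumed 40/20 dropout split, the spurious advantage to the arm with shorter follow-up is about 1 to 7 points over true risks of 10% to 90%. In the other conditions worked through above it is smaller or zero. With equal 30% loss there is no bias towards either arm, only mild dilution of a true difference (20 points becomes 17.7). The documents give no ground for saying which arm will lose more, or that harm will be concealed. This is a cheap improvement to the safety analysis, not a flaw that undermines it.

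**What to change.** In SAP 9.5.1:
1. Restore time to first event by arm for any AE, any SAE and any related AE, from first dose, with censoring at the last contact at which AEs were assessed or at Week 14, whichever comes first.
2. Add events per person-time by arm.
3. Report AE follow-up time by arm, so that a reader can see whether it differs.
4. Keep the proportions and the risk difference alongside.
5. State one AE window. SAP 3.1.1 says 8 weeks, SAP 9.5.1 says the duration of the study, and Protocol 8.3 collects to Week 14; the censoring rule needs this settled.

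If the team prefers not to run the hazard comparison, the SAP should record the departure from Protocol 10.4.4 and the reason.

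The cost is modest programming and one more safety table. AE onset times are collected (Protocol 8.3), and AE and assessment dates are in the database (Protocol 13.4). The limitation is that censoring is assumed unrelated to AE risk, so the analysis does not correct for dropout driven by AEs and should be described accordingly.

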10.4.5 ADHERENCE AND RETENTION ANALYSES

To assess medication adherence, blood samples collected at study Week 8 and Week 12 will be tested for buprenorphine and its metabolite, norbuprenorphine, using quantitative assessments. We will also incorporate a self-report medication adherence CRF that will be completed at each study visit. Results of pill counts will be summarized over time by treatment group.

10.4.6 BASELINE DESCRIPTIVE STATISTICS

Prior to the formal analysis of outcomes, all data will be examined using summary statistics (e.g., mean, standard deviation, median, etc.) and statistical graphs. Demographic variables (e.g., age, gender, race/ethnicity, etc.) will be compared between treatment groups using t-tests for continuous data and chi-square tests for categorical data. If necessary, non-parametric tests will also be used to compare demographic variables between treatment groups. Significant demographic variables will be included in all subsequent models.

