7.2 Adjustments for Covariates

Since this is a randomized, double-blind, placebo-controlled study with equal balance in the treatment arms, no adjustment for demographic or baseline characteristics is planned. However, any assessment of the impact of covariates or adjustments for them will be done in an exploratory manner only and described in the study report.

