8.4 Demographic and Baseline Characteristics

All data collected at baseline will be summarized descriptively for the entire efficacy (intent-to-treat) population. Demographic variables of interest include, but are not limited to, age (years), gender, race and ethnicity, veteran status, service-connected disability, and education level.

Baseline efficacy variables include, but are not limited to CAPS-5, PCL-5, %HDD, PHQ-9, and VR-12.

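### Protocol 10.4.6 adds chance-imbalanced demographics to every model, the SAP confines the primary model to the stratification factors, and neither document says which prevails

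*Protocol*

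**What the plan says.** **Protocol.** Section 10.4.6 says that, before outcomes are analyzed, demographics "will be compared between treatment groups using t-tests for continuous data and chi-square tests for categorical data", with non-parametric tests if needed. It gives age, gender and race/ethnicity as examples and leaves the list open. It sets no significance level. It then states: "Significant demographic variables will be included in all subsequent models". Section 10.4.2 describes the primary model as containing treatment, visit, gender, site, "presence/absence of anti-depressants, and other potential confounders as explanatory variables". The same open-ended reference to other confounders appears twice more in 10.4.2, for the two component outcomes, and once in 10.4.3.

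**SAP.** Section 7.2 says "no adjustment for demographic or baseline characteristics is planned", and that covariate assessments or "adjustments for them will be done in an exploratory manner only and described in the study report". Section 7.1 generally adjusts only for the randomization factors. Section 9.3 and its SAS code give the primary model as treatment, visit, treatment-by-visit, gender, site and antidepressant use, with a random participant effect. On baseline data, section 8.4 says "All data collected at baseline will be summarized descriptively for the entire efficacy (intent-to-treat) population" and specifies no between-arm test.

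**Precedence.** Protocol 10.1 says that analysis will be guided by the SAP, which is to be finalized before lock and unmasking. Protocol 10.4.1 defers covariate details to the SAP, but only for secondary analyses. No section of either document says which prevails on the primary model, and the SAP's version table records no change on this point.

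**The concern.** The 10.4.6 sentence covers all later models, so it reaches the primary one. A statistician following the protocol and one following the SAP could fit different models to the trial's single primary hypothesis test (SAP 7.7).

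The selection principle is a separate problem. If randomization was carried out properly, a significant difference between arms at baseline is a chance event. The test says nothing about whether the variable predicts response, so the rule can admit a variable with no prognostic value and leave out one that has it.

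The choice matters for the estimate as well as the p-value. In a logistic model the treatment odds ratio is conditional on the covariates included, so its value, and what it estimates, can shift with the covariate set.

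Timing adds to this. Comparing arms requires knowing each participant's group, and SAP 4.4.2 withholds assignment until after database lock, apart from emergencies. Under 10.4.6 the covariate list therefore cannot be settled while the trial is masked.

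**Working it through.** **1. The plan's own figure.** The documents give no figure for the covariate rule. The nearest is the primary power of 0.560 in protocol 10.5 (5/45 against 14/45, Fisher's exact test with the Walters approximation, two-sided 0.05). It reproduces:

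- arcsin√(14/45 − 1/90) − arcsin√(5/45 + 1/90) = arcsin√0.3000 − arcsin√0.1222 = 0.5796 − 0.3571 = 0.2225
- 0.2225 × √90 = 2.11, and 2.11 − 1.96 = 0.15
- Φ(0.15) = 0.560

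This figure takes no account of covariates and does not change here.

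**2. The two primary models side by side.**

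| Term | Protocol 10.4.2 and 10.4.6 | SAP 7.1, 7.2, 9.3 |
|---|---|---|
| Treatment, visit, treatment-by-visit | yes | yes |
| Site, gender, antidepressant use | yes | yes |
| Demographics significant between arms | yes | no (exploratory only) |
| Other unnamed confounders | yes | no (exploratory only) |

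**3. How many variables could enter by chance.** Gender is a stratification factor and is already in both models, so it cannot be newly added.

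- Protocol examples without gender: age and race/ethnicity. That is k = 2, or 3 if race and ethnicity are tested separately.
- SAP 8.4 list: "age (years), gender, race and ethnicity, veteran status, service-connected disability, and education level". Without gender, k = 5, or 6 with race and ethnicity separate.

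**4. Chance of at least one entry.** Assumptions, which are not in the documents: a 0.05 threshold and independent tests. The formula is 1 − 0.95^k.

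| k | Source | Chance |
|---|---|---|
| 2 | protocol examples | 1 − 0.9025 = 9.8% |
| 3 | protocol examples, race and ethnicity split | 1 − 0.8574 = 14.3% |
| 5 | SAP list | 1 − 0.7738 = 22.6% |
| 6 | SAP list, race and ethnicity split | 1 − 0.7351 = 26.5% |
| 10 | illustrative, since both lists are open-ended | 1 − 0.5987 = 40.1% |

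Under the SAP 9.3 list the corresponding chance is zero, because no baseline test feeds the model. Independence is doubtful for pairs such as veteran status and service-connected disability. Positive dependence lowers the figures, with a floor of 5% if all the tests were perfectly dependent.

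**5. Type I error.** This was checked by simulating 15,000 null trials per setting, with 45 per arm and a linear model. With five covariates, at least one was added in 22.4% and 22.8% of trials, in line with step 4. The rejection rate under the protocol rule was 0.043 to 0.048 across the settings (one or five covariates, and a correlation of 0, 0.3 or 0.5 between one covariate and the outcome). The Monte Carlo standard error is about √(0.05 × 0.95 / 15,000) = 0.002. There was no inflation. The planned logistic mixed model was not simulated.

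**The case against.** The strongest reply is that the SAP settles the matter. It is the more detailed document, protocol 10.1 points to it, and section 9.3 gives a closed list of terms with code. Section 7.2 also labels any other adjustment exploratory, which weakens a claim that a protocol-selected covariate set is primary. Most of this stands. A reader might infer that the primary model is not fixed before unmasking, or that either covariate set could be chosen freely once results are known. The documents do not support that. The SAP model is set out in advance, apart from its own non-convergence provisions in 7.1, and the 10.4.6 rule works on baseline data, not outcomes. What remains is that precedence is only implied and the conflicting protocol sentence is still in force.

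A reader might also put the chance of a lucky entry at 30%, by counting seven SAP demographics (1 − 0.95^7 = 0.302). That counts gender, which is already in the model. It also applies the protocol's testing rule to a list that the SAP only describes.

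Finally, a reader might argue that extra terms would overload a model expecting only 5 + 17 = 22 Week 8 responders. That count belongs to one power scenario, and the mixed model also uses Weeks 4 and 12. No loss of precision has been calculated.

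**Conclusion.** The protocol text is wrong as written, and the two documents need reconciling. They specify different primary models, and the protocol's version selects covariates by chance imbalance instead of prognostic value, at a point when group membership must be known.

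The chance that luck alone adds at least one demographic is about 10-14% on the protocol's own examples and 23-26% on the SAP's list. Both ranges assume a 0.05 threshold, independent tests and the exclusion of gender. The protocol states no threshold and neither list is closed, so these are illustrations and not properties of the plan.

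A reader might infer that the rule inflates the false-positive rate. Nothing here shows that, and the linear-model check found no inflation. The harm is that the primary model and its effect estimate depend on chance imbalance and on which document the analyst follows.

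**What to change.** - In protocol 10.4.6, delete the last sentence and the between-arm significance tests of baseline variables, so that the section matches the descriptive reporting already in SAP 8.4.
- In protocol 10.4.2 (three places) and 10.4.3 (one place), delete the open-ended reference to other confounders.
- State the SAP 9.3 covariates in both documents: site, gender and antidepressant use, alongside treatment, visit and treatment-by-visit. Say that any other adjustment is exploratory.
- Any further covariate, such as baseline CAPS-5 or baseline drinking level, is an optional design choice. If one is wanted, name it in both documents before unmasking and justify it by its prognostic value.

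The cost is a text amendment. It needs no new data and does not change the stated sample size or power, which are unadjusted.
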